2.1.3.1 Primary efficacy endpoint(s)

The primary efficacy endpoint is the percentage (%) of time of glucose concentrations within the range of 70-180mg/dL (3.9–10mmol/L) during Week 16, as obtained by CGM on randomized period.

The percentage of time glucose in target range 70-180mg/dL (3.9–10mmol/l) during weeks 15-16 (obtained from CGM) will be calculated based from the denominator of total time with valid data.

During Week 15, each patient wears the CGM device for 7 consecutive days to generate at least 4 days of useable CGM records for the primary efficacy endpoint assessment. If a patient fails to provide at least 4 days (not necessarily consecutive) of useable CGM data over the 7-day CGM performance, he/she repeats the CGM performance during Week 16.

2.1.3.2 Secondary efficacy endpoint(s)

The main secondary efficacy endpoints include:

- Incidence and rate of nocturnal symptomatic hypoglycemia, defined as an event with typical symptoms of hypoglycemia accompanied by SMPG ≤ 70 mg/dL (3.9 mmol/L) that occurs between 00:00 and 05:59 hours,
- The mean change of each participant's glucose level during the last four hours of CGM data collection prior to next day's basal insulin injection ([1](#)),
- Percentage (%) of time glucose concentrations obtained by CGM within target range of 70-140 mg/dL (3.9–7.8 mmol/L) during the last 4 hours of CGM data collection prior to next day basal insulin injection,
- Total, within day and between day CV% in glucose values obtained from CGM.

Testing strategy of the six main secondary endpoints can be found in [Section 2.4.4.3](#).

The other secondary efficacy endpoints include:

- Frequency and distribution (nocturnal or 24 hours) of all hypoglycemia events analyzed by hypoglycemia categories (severe, documented symptomatic, asymptomatic, probable and relative) as defined in the publication ADA Workgroup on Hypoglycemia, 2015 (see [Appendix A](#)),
- Additional CGM endpoints (data obtained at Week 16):
 - Percentage (%) of time glucose concentrations within the target range of 70-140 mg/dL (3.9–7.8 mmol/L), analyses on all-time (24 hours) CGM data.
 - Percentage (%) of time in hypoglycemia defined as percentage time with glucose concentrations < 70 mg/dL (3.9 mmol/L) and < 54 mg/dL (3 mmol/L), analyses on both all-time (24 hours) and nocturnal (00:00–05:59 h) CGM data
 - Percentage (%) of time in hypoglycemia defined as percentage time with glucose > 140 mg/dL (7.8 mmol/L), > 180 mg/dL (10 mmol/L) and > 250 mg/dL (13.9 mmol/l), analyses on both all-time (24 hours) and nocturnal (00:00–05:59 h) CGM data.

- Area under the curve (AUC) of glucose concentration <70 mg/dL (3.9 mmol/L), derived as the area below 70 mg/dL (3.9 mmol/L) and above the CGM profile (ie, the median curve), divided by the length of the evaluable assessment interval. The median curve will be obtained by superimposing the date-time-stamped glucose values collected by CGM into 24 nominal hourly baskets from which the point-wise median is calculated. For each patient, each evaluable day will have a glucose-time profile curve calculated. The AUC of glucose concentration <70 mg/dL (3.9 mmol/L) will be calculated for each patient day median curve. The mean AUC of glucose concentration <70 mg/dL (3.9 mmol/L) from each patient's all evaluable days will be used for further analysis.

- AUC of glucose concentration >180 mg/dL (10 mmol/L), derived as the area above 180 mg/dL (10 mmol/L) and below the CGM profile (ie, the median curve), divided by the length of the assessment interval. The median curve will be derived as defined previously.

Weighted mean 24-hour glucose, calculated by area under the median curve divided by the length of the evaluable assessment interval. The median curve will be derived as defined previously.

- other CGM glucose variability parameters include

(1) Total, within day and between day standard deviations (SDs).

$SD_{total} = \sqrt{\frac{\sum (x_i - \bar{x})^2}{k-1}}$, where x_i is individual glucose reading, \bar{x} is the mean glucose readings from all evaluable CGM data points from all evaluable CGM profiles for the same visit. k is number of CGM data points.

$SD_{within} = \sqrt{\frac{\sum (x_i - \bar{x}_j)^2}{h-1}}$, where x_i is individual CGM data points within the CGM profile, \bar{x}_j is the mean glucose readings from all CGM data points within the CGM profile. h is number of CGM data points. For each patient and visit, the within standard deviations from all CGM profiles will be averaged as the final value of the within standard deviation for the visit.

$SD_{between} = \sqrt{\frac{\sum (\bar{x}_j - \bar{x})^2}{m-1}}$, where m is the number of evaluable CGM profiles.

(2) Mean amplitude of glycemic excursions (MAGE), defined as mean glucose value by summing absolute rises and falls (local minima and maxima) of more than 1 SD. It includes only peak-to-nadir or nadir-to-peak excursions. $MAGE = \sum \frac{\lambda}{n}$ if $\lambda > SD$, where λ is the glucose increase or decrease (peak-to-nadir or nadir-to-peak excursions). n is the number of peak-to-nadir or nadir-to-peak excursions.

(3) Distance traveled (DT), defined as the sum of the absolute difference in glucose levels from the consecutive glucose measurements in the 24-hour CGM

profile. $DT = \frac{\sum |x_i - x_j|}{k^*}$, where x_i and x_j are the two consecutive glucose measurements in the 24-hour CGM profile, and k^* is the number of the absolute differences in glucose levels.

(4) Total area under the curve (AUC), calculated by area under the median curve. The median curve will be derived as defined previously.

(5) Continuous overall net glycemic action (CONGA), defined as calculated as the SD of the summated differences between a current observation and an observation n hours previously. For this study, $n=1, 2, 4$ or CONGA-1, CONGA-2, CONGA-4

will be calculated. $\sqrt{\frac{\sum (D_i - \bar{D})^2}{k^{**} - 1}}$, where D_i is the difference between glucose reading at time t and t minus n hours ago from the 24-hour CGM profile and \bar{D} is the mean difference. k^{**} is the number of D_i included in the 24 hour CGM profile.

- 7-point SMPG profiles (pre-prandial and 2-hour postprandial plasma glucose at breakfast, lunch and dinner, and bedtime),
- Change from baseline to study endpoint in HbA1c,
- Change from baseline to treatment period endpoint in central lab FPG,

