11.4.2 Analyses of efficacy endpoints

11.4.2.1 Analysis of primary efficacy endpoint(s)

The percentage of time plasma glucose within target range of 70-180 mg/dL (3.9–10 mmol/L) during Weeks 15-16 (obtained from CGM) will be calculated based on the total time within glycemic range in the evaluable assessment interval, divided by the total time of the evaluable assessment interval.

The evaluable assessment interval for the calculation will comprise of 24-hour periods during Weeks 15-16 for which there is sufficient non-missing data. In order to be evaluable for analysis, a patient needs at least 4 days of 24-hour data meeting this criterion and should not receive protocol prohibited medication.

The endpoint will be summarized by treatment group using mean, median, standard deviation, minimum and maximum.

Differences between treatment groups will be explored using a generalized linear model, adjusting for key baseline characteristics (duration of diabetes, BMI, age and baseline value) and randomization strata. Adjusted mean estimates for each treatment with standard errors, the adjusted estimate of treatment mean difference with standard error and a 95 % confidence interval for the treatment mean difference will be provided. The statistical test will be for superiority of Toujeo over Lantus, two-sided and at a 5% significance level.

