The percentage of time plasma glucose in target range 70-140 mg/dL (3.9–7.8 mmol/L), and the percentage of time plasma glucose \leq 70 mg/dL (3.9 mmol/L) and \leq 54 mg/dL (3 mmol/L) will be calculated and analyzed as for the primary endpoint. For these endpoints, the time period of observation will be all evaluable time (24hours) and nocturnal, where nocturnal is defined as the period between 00:00-05:59 within the evaluable assessment interval.

The area under the curve (AUC) of glucose concentration ≤70 mg/dL (3.9 mmol/L) will be derived as the area above the CGM profile (ie, the median curve) and below this lower limit of the glycemia range, divided by the length of the evaluable assessment interval. The median curve will be obtained by superimposing the date-time-stamped glucose values collected by CGM into 24 nominal hourly baskets from which the point-wise median is calculated.

The AUC of glucose concentrations >180 mg/dL (10 mmol/L) will be derived as the area below the CGM profile (ie, the median curve) and above the upper limit of the glycemia range, divided by the length of the assessment interval. The median curve will be derived as defined previously.

All of the continuous CGM endpoints will be summarized, and will be analyzed using a generalized linear model as described for the primary endpoint.

The absolute values and change in 7-point SMPG profiles (pre-prandial and 2-hour post-prandial plasma glucose at breakfast, lunch and dinner, and bedtime) from baseline to Week 12, Week 16 and the last on-treatment value (study endpoint) will be presented descriptively by treatment group.

Summary statistics will also be presented for the absolute values and the change from baseline in HbA1c and central lab FPG to Week 8, Week 16 and last on-treatment value (study endpoint). The change from baseline to study endpoint will be analyzed using a mixed-effect model with repeated measures (MMRM) approach under the missing at random framework, using an adequate contrast at endpoint. The model will include fixed categorical effects of treatment arm, visit, treatment-by-visit interaction, randomization strata, and baseline HbA1c as covariate as well as baseline HbA1c-by-visit interaction.

Insulin dose (total daily dose (units, units/kg), basal, mealtime/bolus, ratio of basal to bolus insulin dose) will be descriptively summarized for absolute values and change from baseline.

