7. Per protocol, during Week 15, patients will wear a blinded CGM device for 7 consecutive days to generate minimum 4 days of useable CGM data. If a patient fails the first attempt for any reason, he/she will be retrained for CGM conduct and complete another course of blinded CGM in Week 16. If the patients fails the first week of CGM, only the second week CGM data will be used for data analysis and determine whether there are sufficient data to derive CGM variables per steps 1-6 above. If the second week of CGM data are not sufficient per steps 1-6 above either, CGM data from the first week and the second week will be pooled together to repeat steps 1-6.
8. If a patient prematurely withdraws from the study before Week 15 (visit 18) the CGM data will be missing for the individual patient and the patient will be excluded from the primary efficacy analyses.
9. For all CGM parameters except the total and between day coefficient of variations (CV%) and standard deviations and area under the curve of glucose concentrations, a CGM parameter will be first calculated based on each 24-hour CGM profile from the visit, the final values of the CGM parameters for the visit will be based on the average of parameter values taken on each CGM profile from each CGM visit.

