2.4.4 Analyses of efficacy endpoints

2.4.4.1 Analysis of primary efficacy endpoint(s)

The percentage of time glucose in target range 70-180mg/dL (3.9–10mmol/l) during week 16 (obtained from CGM) will be calculated based from the denominator of total time with valid data. The criteria to evaluate baseline and Week 16 CGM data are in Section 2.1.3.

The evaluable assessment interval for the calculation will comprise of 24-hour periods during Week 16 for which there is sufficient non-missing data. In order to be evaluable for analysis, a patient needs at least 4 days of 24-hour data meeting this criterion and should not receive protocol prohibited medication.

The endpoint will be summarized by treatment group using mean, median, standard deviation, minimum and maximum.

Differences between treatment groups will be assessed using a generalized linear model with identity link, adjusting for key baseline characteristics (duration of diabetes, baseline BMI, age and baseline value) and randomization strata if model permits. If model does not converge, for example due to over 90% patients fall into the carbohydrate counting, the specific factors which cause non convergence may be dropped from the model. Adjusted mean estimates for each treatment group with standard errors, the adjusted estimate of treatment mean difference with standard error and a 95 % confidence interval for the treatment mean difference will be provided. The statistical test will be for superiority of Toujeo over Lantus, two-sided and at a 5% significance level.

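### As written, weighted mean 24-hour glucose and AUC below 70 mg/dL divide the area of a 24-hour curve by a multi-day interval; the divisor needs to be defined as the length of the curve (minor)

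*SAP*

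**What the plan says.** **The curve.** SAP 2.1.3.2 builds the median curve by "superimposing the date-time-stamped glucose values collected by CGM into 24 nominal hourly baskets from which the point-wise median is calculated". It therefore covers one nominal day.

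**The divisor.** Weighted mean glucose is "Weighted mean 24-hour glucose, calculated by area under the median curve divided by the length of the evaluable assessment interval". AUC below 70 mg/dL has the same divisor in the SAP and in Protocol 11.4.2.2, where the area is "divided by the length of the evaluable assessment interval". AUC above 180 mg/dL is divided in both documents by the length of an assessment interval, without the word evaluable, and that shorter term is not defined. Total AUC, also in SAP 2.1.3.2, has no divisor.

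**The definition.** The interval is defined once in each document, under the primary endpoint. SAP 2.4.4.1: "The evaluable assessment interval for the calculation will comprise of 24-hour periods during Week 16 for which there is sufficient non-missing data". Protocol 11.4.2.1: "The evaluable assessment interval for the calculation will comprise of 24-hour periods during Weeks 15-16 for which there is sufficient non-missing data". Both then require at least 4 such days.

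**Per day or pooled.** For AUC below 70 mg/dL the SAP adds: "For each patient, each evaluable day will have a glucose-time profile curve calculated". The AUC "will be calculated for each patient day median curve" and is then averaged over the evaluable days. Protocol 11.4.2.2 has no per-day step. Item 9 of the CGM criteria in SAP 2.1.3 says that "a CGM parameter will be first calculated based on each 24-hour CGM profile from the visit" and then averaged over profiles. It exempts total and between-day CV and SD, and area under the curve. Weighted mean glucose is not named among the exceptions.

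**The concern.** The numerator covers 24 hours. The divisor, if looked up where it is defined, covers several days. The result is then not a mean glucose or a time-averaged excess over a threshold. It is that quantity divided by the patient's number of usable days, so it depends on how much of the CGM wear qualified.

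A weighted mean glucose around 30 mg/dL would be noticed at once. AUC below 70 and AUC above 180 have no familiar size, so the same slip could pass there. These endpoints are analysed with the primary-endpoint model, which adjusts for the baseline value. A baseline value scaled by its own, possibly different, day count would add to the confusion.

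**Working it through.** The documents give no numerical value for these endpoints, so there is no result of the plan's own to reproduce. The check is of dimensions.

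**Inputs**
- Length of the median curve: 24 h (24 hourly baskets, SAP 2.1.3.2).
- Evaluable assessment interval: m qualifying days, about 24m hours, with m at least 4 (SAP 2.4.4.1, Protocol 11.4.2.1).
- A qualifying day runs from midnight to midnight. An end fragment counts only with at least 245 readings (SAP 2.1.3). This threshold reproduces: 0.85 × 288 = 244.8, rounded up to 245.
- Wear is 7 days, with the sensor inserted at the visit (Protocol 10.2.4.1). Onsite visits are in the morning (Protocol 10).
- Assumed for illustration only: a flat glucose of 160 mg/dL.

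**Step 1: the literal formula.** With curve area A, A/(24m) = (A/24)/m. The value is too small by exactly m, whatever the glucose level. For 160 mg/dL, A = 160 × 24 = 3,840 mg/dL·h:

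| Usable days m | Divisor (h) | Literal value (mg/dL) | With 24 h (mg/dL) |
|---|---|---|---|
| 4 | 96 | 40.0 | 160 |
| 5 | 120 | 32.0 | 160 |
| 6 | 144 | 26.7 | 160 |

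For the same glucose, 4 against 6 usable days gives 40.0/26.7 = 6/4 = 1.5.

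**Step 2: AUC below 70.** The SAP averages daily values over m days. If each daily area A_d is also divided by 24m, the result is (1/m) Σ A_d/(24m) = (mean of A_d/24)/m. The number of days is divided out twice.

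**Step 3: the range of m.** Insertion at 07:00 leaves a first-day fragment of 17 h = 204 readings and a last-day fragment of 7 h = 84. Insertion at 12:00 leaves 144 and 144. Neither end reaches 245, so one wear yields at most 6 days. Two weeks are pooled only when each falls short of 4 days (SAP 2.1.3, item 7), which gives at most 3 + 3 = 6. The usual range is therefore 4 to 6.

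**Step 4: the 24-hour divisor.** One simulated patient had six days of 5-minute readings (a daily wave around 160 mg/dL plus noise; all assumed) and a true mean of 163.0 mg/dL.
- Divided by 24 h, the per-day curves averaged 162.4 and the pooled curve gave 163.1.
- Divided by 144 h, they gave 27.1 and 27.2.
- AUC above 180 over 24 h was 14.4 per day and 10.7 pooled.

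The divisor decides whether the scale is right. For the threshold areas, per-day and pooled curves are also not interchangeable.

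**The case against.** The best defence is that 24 hours was meant all along. The multi-day definition is written for the primary calculation. The SAP gives each evaluable day its own curve, and the natural interval for a one-day curve is that day. Item 9 calculates CGM parameters per 24-hour profile, and its exceptions do not name weighted mean glucose. This has weight: a 24-hour divisor is the likelier intention, and a reader who inferred that the endpoints will certainly be reported several times too small would go beyond the documents.

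It does not remove the problem. Both documents reuse the term in its multi-day sense for other endpoints, when they place the nocturnal hours within it (SAP 2.4.4.2, Protocol 11.4.2.2). Item 9 does not alter the divisor, and it exempts AUC from per-profile calculation, whereas SAP 2.1.3.2 prescribes exactly that for AUC below 70. The protocol describes one superimposed curve over the multi-day interval. A programmer has to override the written formula to reach 24 hours.

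Other stronger readings also fail:
- **A factor of 7.** Step 3 rules this out for a single morning-started wear. SAP 2.4.4.2 provides for more than 7 evaluable days, but for a different endpoint.
- **All AUC endpoints.** Total AUC has no divisor. For AUC above 180 the fault is an undefined term, most naturally read the same way.
- **A large loss of precision.** The between-patient CV c is inflated by √(1 + v² + v²/c²), where v is the CV of 1/m. Equal thirds at 4, 5 and 6 days give v² = 0.0278; 5%, 10% and 85% give v² = 0.0133. If c for the threshold areas is 0.5 to 1.5 (assumed), the inflation is only 1.01 to 1.07. It would be larger for weighted mean glucose, where the error would be seen.
- **Bias between arms.** This needs usable days to differ by arm, which nothing in the documents shows.

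**Conclusion.** The point holds as a fault in the written formula. Read with the only definition available, weighted mean 24-hour glucose and AUC below 70 are too small by the number of usable days, usually 4 to 6, and vary with it by up to a factor of 1.5. That factor does not depend on the assumed glucose level. AUC above 180 rests on an undefined interval. A 24-hour divisor was probably intended, but the text does not settle it, and the per-day instructions in SAP 2.1.3 and 2.1.3.2 contradict each other.

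The consequence is limited. These are other secondary endpoints, for which SAP 2.4.4.3 gives nominal p-values for information only. The primary endpoint and the seven-step hierarchy are untouched. Minor priority.

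**What to change.** In SAP 2.1.3.2, state for weighted mean glucose, AUC below 70 and AUC above 180 that each area is divided by the length of the curve from which it is taken: 24 hours, or the recorded hours of that day's profile if the area covers only those hours. Calculate the value for each evaluable day and average over the patient's evaluable days, at baseline and at endpoint alike.

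Amend the AUC exemption in item 9 of SAP 2.1.3 so that it agrees. Protocol 11.4.2.2 carries the same divisor with a superimposed curve, so list the clarification among the modifications in SAP 1.5 or 1.6.

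The cost is a few sentences across three formulas and one rule. No new data are needed, and nothing confirmatory changes. If 24 hours was always intended, the change only records it. The choice between per-day and pooled curves does alter the threshold areas, so it should be fixed in writing before database lock.

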2.1.3.2.1 Hypoglycemia

2.1.3.2.1.1 Hypoglycemia classification

Hypoglycemia observation periods

- **Pre-treatment hypoglycemia events** are events that occur during the pre-treatment period
- **Treatment-emergent hypoglycemia events** are events that occur during the on-treatment period
- **Post-treatment hypoglycemia events** are events that occur during the post-treatment period

Hypoglycemia events will be categorized as defined in [Appendix A](#). The glucose values used to classify hypoglycemia events are from the hypoglycemia e-CRF rather than the glucose values from CGM or central laboratory.

The incidence (proportion of patients with any hypoglycemia events) and the rate (number of events per patient year of exposure) will be assessed during each safety observation period for each hypoglycemia category.

In case of some classification items are missing (i.e. assistance required or not, presence of symptom, glycemic values, use of countermeasure) to determine hypoglycemia classification (see Section 2.5.3) the following categories will be presented.

- Not classified – non severe
- Not classified – severity unknown

2.1.4 Safety endpoints

Adverse events (AEs) spontaneously reported by the patient or observed by the Investigator, will be monitored.

The following safety parameters will be analyzed in this study:

- Adverse events, serious adverse events including injection site and hypersensitivity reactions
- Vital signs, including body weight
- Hypoglycemia

Observation period

For all safety data, the observation period will be divided into three segments:

- The pre-treatment phase is defined as the time between when the patients give informed consent and time of the first IMP administration (excluded).
- **Treatment-emergent AEs (TEAEs)** are AEs that developed or worsened or became serious during the on-treatment period.
- The on-treatment phase is defined as the time from the first IMP administration (included) until 1 day after the last dose of IMP (until midnight of day after last IMP dosing day).
- The post-treatment phase is defined as the time after the on-treatment phase until the end of treatment.

2.1.4.1 Adverse events variables

All AEs and SAEs will be coded to a “Lower Level Term (LLT)”, “Preferred Term (PT)”, “High Level term (HLT)”, “High Group Level Term (HLGT)” and associated primary “System Organ Class (SOC)” using the version of MedDRA (Medical Dictionary for Regulatory Activities) currently in effect at the sponsor at the time of database lock. MedDRA terms for hypersensitivity and injection site reactions will be included

The occurrence of AEs and SAEs is recorded from the time of signed informed consent until the end of the study. If an AE/SAE is ongoing and not resolved by the end of the study observation period (defined as the time from randomization until the end of the study) and leads to subsequent death of the patient, it will have to be reported.

